EXPERIMENTAL PROTOCOL

Amendment 2.1

(Country-specific protocol amendment for US sites)

1. GENERAL INFORMATION**Title:** ThRombosis exclUsion STudy for STA® - Liatest® D-Di XL**Brief title:** TRUST**Study product:** STA® - Liatest® D-Di XL – an immuno-turbidimetric in vitro diagnostic (IVD) assay for the quantitative determination of D-dimer in venous plasma**Coordinating investigator authorized to sign the protocol:** [name], MPH, Massachusetts General Hospital, Boston, MA (US)**Centers:** between 10 and 25 investigation centers in Europe, US and Canada**Participating investigators:** Physicians at each center – site list will be provided separately**Sponsor:** DIAGNOSTICA STAGO S.A.S

[name]

Representative of the sponsor authorized to sign the protocol:

[name], Market Access – Clinical Affairs Specialist

Monitoring, Data Management and Statistics:Donawa Lifescience Consulting S.r.l
[name]
[name]
Tel: [name] Fax: [name]

Revision History:

[figure not shown]
Version	Description	Date
1.0	First release	11 January 2018
1.1 Country specific amendment for France	
Modifications specific to France requested by the central Ethics Committee (CPP Sud Méditerranée II):
 
 - §6.1. Clarification that screening logs may be used in the study but will not be mandatory - §6.7. Clarification of the timing of the 3 month follow-up - §14.7. and 14.8. Modifications related to GDPR regulation. 
Update of title of Donawa personnel involved in the study
	08 August 2018
2.0	
Number of evaluable reference-positive subjects to be enrolled increased from 100 to 115. Consequently, taking into consideration observed prevalence, number of suspected PE and/or DVT subjects expected to be enrolled increased from 2,848 to 3,538. The expected enrolment of US vs out of US patients was updated based on actual enrolment data.
 
Statistical sections updated:
 
 - §9.5. Entire section updated - §9.6. NPV and Sensitivity testing hypothesis updated 
Typo correction throughout the protocol.
	04 September 2019
2.1 Country specific amendment for US sites	
 - Revision of Section 8.1 to allow remote monitoring activities - Revision of Sec 14.1, to allow verbal consent procedure in clinical sites where local COVID-19 Infection Control Guidelines discourage transfer of hardcopy paper between research staff and patients (to minimize the risk of viral transmission) - Modifications of sections 9.5 to include completion of PE part of the study and update of sample size based on observed prevalence. 	24 August 2020

PROTOCOL – SUMMARY	
Study type: Prospective, non-randomized, non-interventional, multicenter diagnostic accuracy study in a standard of care setting.	
Test product: STA® - Liatest® D-Di XL – an immuno-turbidimetric in vitro diagnostic (IVD) assay for the quantitative determination of D-dimer in venous plasma	
Regulatory status of the product: EUROPE: The product is not CE marked US: The product is not approved for commercial use	
Coordinating investigator: [name], MPH, Massachusetts General Hospital, Boston, MA (US)	
Centers: between 10 and 25 investigation centers in Europe, US and Canada.	
Sponsor: DIAGNOSTICA STAGO S.A.S [name]	
Primary objective: To demonstrate the ability of STA® - Liatest® D-Di XL combined with a clinical PreTest Probability (PTP) to safely exclude pulmonary embolism (PE) and deep venous thrombosis (DVT) as measured by Negative Predictive Value (NPV) and sensitivity.	
Primary endpoint: For each "unlikely" [*] subject, Venous ThromboEmbolism (VTE) diagnosed dichotomously (positive/negative) by: 
• Reference Standard, which includes data obtained by imaging or follow-up,• Device (STA® - Liatest® D-Di XL)	
* Subjects with low or moderate pre-test probability as determined by Wells score are collectively labeled "unlikely"	
Secondary objectives: 
1. To estimate additional STA® - Liatest® D-Di XL accuracy parameters, including specificity and positive predictive value (PPV)2. To constitute a plasma bank to be used for future studies with other DDi assays under development by Stago.	

Study design

[figure not shown]
The study will be conducted in two phases:

- 1) The initial phase (see diagram below) will include sample and data collection from subjects suspected of VTE (PE and/or DVT) at participating sites (“enrolling sites”); subjects will be diagnosed and treated in accordance with routine standard of care (SOC). A test using VIDAS® D-Dimer Exclusion II™ (VIDAS) assay will be conducted on one of the frozen plasma aliquots. The result obtained (i.e. D-Di “reference value”) will be used in the following phase to assess sample stability.

- 2) When the STA® - Liatest® D-Di XL product is ready for clinical testing (see diagram below), frozen samples from unlikely patients will be tested with VIDAS assay and with STA® - Liatest® D-Di XL. The results of the VIDAS assay will be used to assess samples stability. The results from “stable” samples will be used for comparison to reference (imaging or follow-up) and computation of accuracy parameters (sensitivity, NPV, specificity and PPV). STA® - Liatest® D-Di XL and stability testing will be performed at selected sites (“testing sites”). There will be at least 2 testing sites in the US and 2 in Europe.

Procedures for STA - Liatest DDi XL clinical testing

Main inclusion criteria: The study population will be recruited from prospective, consecutive, ambulatory outpatients (presenting at the emergency unit or outpatient clinic) suspected of having VTE. Patients with DVT and PE will be analyzed as separate groups. Therefore, enrolment in each group will be monitored separately and will be stopped when the desired target per indication is reached. Subjects suspected of both DVT and PE will be included in both PE and DVT groups.

Number of Subjects

A sample size of $N = 115$ evaluable reference-positive subjects is needed to achieve at least 90% power to demonstrate sensitivity for PE and DVT separately. This will provide at least 80% power to demonstrate co-primary performance goals for PE and co-primary performance goals for DVT. The samples needed to obtain the number of positives will, due to low prevalence, yield a large number of negative subjects so that power for demonstrating NPV performance goals is about 100% in each indication.

Expected overall study enrolment – PE

Based on actual prevalence data obtained during enrolment, a total of at least 2,908 subjects were expected to participate in the PE study—with at least 2,206 from the US and at least 702 from OUS—to have 90% power to demonstrate STA® - Liatest® DDi XL efficacy for PE.

At the time this protocol amendment is issued, a total of 3,054 PE patients were enrolled including 121 PE positive patients (uncleaned, non-final data). Thus, the PE data collection has been completed and data cleaning is in progress.

Expected overall study enrolment - DVT

Enrolment is still ongoing for DVT patients, for which the following estimated enrolments were calculated:

DVT estimated enrolment:

Based on actual prevalence data, a total of 1,870 subjects are expected to participate in the DVT study—with at least 1,032 from the US and at most 568 from OUS—to have 90% power to demonstrate STA® - Liatest® D-Di XL efficacy for DVT.

In summary, the two trials are expected to enroll a total of 4,924 subjects.

Note: some patients might have both PE and DVT indications and, therefore, contribute to both enrolment counts, hence the “at most” mention.

It is important to note that the above sample size is based on specific prevalence assumptions for DVT in the US and OUS. Blind sample size re-estimation has been specified for the DVT study separately to re-calculate sample size during the trial based on prevalence of reference-positive cases. Counting reference-positive will be done blind to STA® - Liatest® D-Di XL outcome.

Total expected duration of the study: around 48 months (from beginning of enrolment to site closure)

Total duration by subject: maximum duration of 4 months

Follow-up: All patients with low or moderate Wells score for whom VTE is excluded as per site standard of care (SOC) will be followed for 3 months to evaluate potential development of DVT and/or PE.

Statistical Considerations

Sample Size Justification: Presentation of the sample sizes noted in the synopsis above is based on meeting performance goals using two-sided, exact binomial 95% confidence intervals based on the following assumptions:

- US prevalence of reference-positive = 3.4% and 5.3% for PE and DVT respectively
- OUS prevalence of reference-positive = 5.7% and 8.1% for PE and DVT respectively
- D-Di XL sensitivity = 98% for both PE and DVT
- D-Di XL NPV = 99.6% for both PE and DVT

Statistical Hypotheses for Co-primary Endpoints: The following co-primary hypotheses are specified separately for PE and DVT:

H_0 : NPV ≤ 0.95

H_1 : NPV > 0.95

and

H_0 : Sensitivity ≤ 0.90

H_1 : Sensitivity > 0.90

Additionally, we will need to show that point estimates for NPV and are sensitivity ≥ 0.97 and ≥ 0.95 respectively in both indications.

TABLE OF CONTENTS

2. STUDY RATIONALE

2.1 JUSTIFICATION OF STUDY IN LIGHT OF CURRENT KNOWLEDGE

It is well known that D-dimer determination can be used in conjunction with a clinical pretest probability (PTP) assessment model to exclude pulmonary embolism (PE) and deep venous thrombosis (DVT) in outpatients suspected of PE or DVT [CLSI H59-A]. Assessment of the initial clinical probability is an essential step in the diagnostic management of PE and DVT [Wells 2000, 2003, Klok 2008, Ceriani 2010].

In this context, the quantitative D-dimer assay has its greatest utility for its negative predictive value (NPV) when applied to patients classified as “unlikely” or “low or moderate” clinical probability. In these patients, a D-dimer result below the exclusion threshold value suggests strongly against the presence of VTE, such that the diagnosis can be confidently excluded and no further diagnostic procedures for VTE (imaging) need to be performed [Perrier 1996, Kelly 2003, BCSH 2004, Goekoop 2007, Pasha 2009].

Diagnostica Stago (henceforth “Stago”) is in the process of developing STA® - Liatest® D-Di XL, a new immuno-turbidimetric assay for the quantitative determination of D-dimer in venous plasma. STA® - Liatest® D-Di XL is an evolution of STA® - Liatest® D-Di, an assay approved in the United States (K964728, K141144, K162227) and Europe for use in conjunction with a clinical pretest probability (PTP) assessment model to exclude pulmonary embolism (PE) and deep venous thrombosis (DVT) in outpatients suspected of PE or DVT.

STA® - Liatest® D-Di XL is expected to have improved precision and analytical measuring range (AMR) compared to STA® - Liatest® D-Di. The new assay includes modifications:

- in the homogenization process of reactional medium containing D-dimer plasma and anti-D-dimer antibodies;
- of the signal processing and calibration both implemented via modifications of the system configuration, and addition of a blocking agent for rheumatoid factor.

STA® - Liatest® D-Di XL is currently undergoing development activities at Stago. Therefore this study will be conducted in two phases:

- 1) The initial phase will include sample and data collection from subjects suspected of VTE (PE and/or DVT) at participating sites (“enrolling sites”); subjects will be diagnosed and treated in accordance with routine standard of care (SOC) (*Note: SOC indicates that the diagnosis and treatment of VTE will be performed according to local practice; i.e. will not be influenced by this study*). Additionally, plasma samples will be collected and frozen in aliquots for later

testing with STA® - Liatest® D-Di XL and to constitute a plasma bank to be used for future studies with other DDi assays under development by Stago.

- 2) When the STA® - Liatest® D-Di XL product is ready for clinical testing, frozen samples from unlikely patients shown to be stable after freezing will be tested with STA® - Liatest® D-Di XL. The result obtained will be used for comparison to reference (imaging or follow-up) and computation of accuracy parameters (sensitivity, NPV, specificity and PPV). STA® - Liatest® D-Di XL and stability testing will be performed at selected sites (“testing sites”). There will be at least 2 testing sites in the US and 2 in Europe. Further details on study design can be found in section 4.2.

2.2 OVERALL RISK/BENEFIT ASSESSMENT

VTE diagnosis and treatment will be conducted in accordance with local standard of care (SOC) at each site.

The additional procedures required for this study are:

- Obtaining additional blood samples (i.e. around 12 ml of whole blood) from enrolled patients at the time of study entry so that plasma can be frozen for later testing with STA® - Liatest® D-Di XL. Plasma aliquots will be used for testing with STA® - Liatest® D-Di XL in this study and for the constitution of a plasma bank for Stago. The plasma bank will be used in future studies to evaluate new D-dimer test products to be used as improved diagnostic tools for DVT and/or PE (currently under development by Stago).
- Obtaining information through 3 months post diagnosis about the occurrence of DVT and/or PE (or other clinical outcomes such as death) in patients for whom VTE was ruled out at the initial visit (i.e. patients with low/moderate PTP score and D-Di negative or with negative imaging at the initial visit).
- For sites not using Wells Score to determine PTP score as part of the SOC for diagnosis of VTE, Wells score will be requested as a study specific procedure at study entry. The Wells score will be implemented in a manner fully consistent with the routine practice at the sites where Wells Score is not part of the SOC diagnosis of VTE (for further details please see section 6). However, at these sites, results of Wells score will *not* be used for diagnosis of VTE which will be performed according to SOC procedures at the site.

As a result, anticipated risks and benefits only include those that are associated with the routine assessment of patients presenting with symptoms suspicious of VTE. Participating in this study does not expose the patients to any additional risk.

3. STUDY OBJECTIVES

3.1 PRIMARY OBJECTIVE AND ENDPOINT

Primary objective:

To demonstrate the ability of STA® - Liatest® D-Di XL combined with a clinical pretest probability (PTP) to safely exclude PE or DVT as measured by Negative Predictive Value (NPV) and sensitivity.

Primary endpoint:

For each "unlikely"¹ subject, VTE diagnosed dichotomously (positive/negative) by:

- Reference Standard, which includes data obtained by imaging or follow-up,
- Tested Device (STA® - Liatest® D-Di XL)

3.2 SECONDARY OBJECTIVES

Secondary objectives:

To estimate additional STA® - Liatest® D-Di XL accuracy parameters, including specificity and positive predictive value (PPV).

To constitute a plasma bank to be used for future studies with other DDi assays under development by Stago.

4. INVESTIGATION PLAN

[figure not shown]
4.1 TYPE OF STUDY

This study is a prospective, non-randomized, non-interventional, multicenter, diagnostic accuracy study in a standard of care setting.

¹ Subjects with low or moderate pre-test probability as determined by Wells score are collectively labeled "unlikely".

4.2 STUDY DESIGN

The study design follows the diagrams shown below and is further described below.

[figure not shown]

1. Subjects suspected of VTE (PE and/or DVT) will be diagnosed and treated in accordance with routine SOC. Sites not using the Wells score as part of SOC will be asked to do it specifically for the study. Additionally, for “unlikely” subjects (with low or moderate PTP), plasma samples will be collected and frozen in aliquots for later testing with STA® - Liatest® D-Di XL and for the constitution of a plasma bank (frozen plasma samples may be used in future studies to evaluate new D-dimer test products to be used as improved diagnostic tools for DVT and/or PE, currently under development by Stago).
2. A test using VIDAS® D-Dimer Exclusion II™ assay (bioMérieux SA, RCS LYON 673 620 399, 69280 Marcy-l'Etoile / France) will be conducted within 6 months on one of the frozen plasma aliquots at “testing sites”: 6 months is a freezing time period not affecting sample stability as declared in the VIDAS package insert. The result obtained (i.e. D-Di value at reference time) will be used in the following phase (see bullet 3) to assess sample stability.

Note that the VIDAS assay was chosen since it is known to provide the best precision among currently approved D-dimer assays [CAP survey 2014, 2015, 2016]. Consequently, using the VIDAS assay is expected to better assess plasma sample stability, which is most efficient for this trial since only stable samples will be included for subsequent testing with STA® - Liatest® D-Di XL.

3. When the STA® - Liatest® D-Di XL product will be ready, clinical testing will be done according to the following diagram.

Procedures for STA - Liatest DDi XL clinical testing

Frozen plasma samples from “unlikely subjects” will be tested with VIDAS assay and with STA® - Liatest® D-Di XL within 4 hours from thawing from the same frozen sample. This measure with the VIDAS assay will be used to assess samples stability. A plasma sample will be considered stable if the result obtained relative to the first testing with the VIDAS assay (“reference value”, see bullet #2) is within:

- +/- 0.15 µg/mL for DDi levels below or equal 1 µg/mL FEU (at first testing);
- +/- 15% for DDi levels above 1 µg/mL FEU (at first testing).

4. For samples determined stable according to defined criteria STA® - Liatest® D-Di XL result, combined with the result of the Wells Score assessment at the first visit, will be used for comparison to reference (imaging or follow-up) and computation of accuracy parameters (sensitivity, NPV, specificity and PPV).

It is important to note that VIDAS assay is used to test stability of frozen plasma samples with respect to D-dimer, *and is not meant to substitute for STA® - Liatest® D-Di XL*. In this context, our interest is in stability as a *characteristic of the sample* (not the device) and is best assessed by VIDAS assay, which is known to provide the greatest precision of cleared products and in this sense can be considered a “reference standard” for sample stability. Only after stability is established it is appropriate to evaluate D-dimer with the test device STA® - Liatest® D-Di XL.

Patients with DVT and PE will be analyzed as separate groups. Therefore, enrolment in each group will be monitored separately and will be stopped when the desired target per indication is reached.

4.3 SITE SELECTION

Investigators participating in the study will be assessed to be qualified by education, training and experience through pre-study visits, publication review and participation to similar studies. Each principal investigator will be contacted to assess what the routine procedure for the diagnosis of VTE is in his/her center. The site will be visited to determine available resources in terms of patient population, site staff and facility structure/organization, unless these information are accessible to Stago otherwise.

Stago plans to include in the study between 10 and 25 sites where patient enrolment will be performed and plasma samples banked frozen (“enrolling sites”). “Testing sites” will be in charge of testing samples, for initial testing with VIDAS assay and with STA® - Liatest® D-Di XL when assay is ready for clinical testing. There will be at least 4 “testing sites”, 2 in Europe and 2 in the US. A “testing site” can also be an “enrolling site”.

Testing of STA® - Liatest® D-Di XL will be performed by site staff blinded to imaging or follow up results. A procedure will be set up before testing starts to ensure that blinding is rigorously maintained at “testing sites”.

4.4 STUDY SITES (CENTERS)

Between 10 and 25 investigation centers in Europe, US and Canada.

5. STUDY POPULATION

5.1 INCLUSION / EXCLUSION CRITERIA

INCLUSION CRITERIA

1. Patient is < 80 years old.
2. Patient presents at least one of these symptoms indicative of proximal DVT or PE:
 - symptoms for **proximal DVT**: leg pain, tenderness (discomfort through palpation), leg swelling, and /or edema,
 - symptoms for **PE**: hemoptysis, lung related chest pain, dyspnea.
3. Patient provides written informed consent to participate in the study
4. Patient is willing to comply with specified follow-up evaluation at 3 months and can be contacted by telephone

EXCLUSION CRITERIA

1. Patient presenting with a condition that may be associated with increased D-dimer levels, even in the absence of VTE, such as:
 - Fibrinolytic therapy within the previous seven (7) days,
 - Disseminated intravascular coagulation
 - Bone fracture or surgery (with general anesthesia longer than thirty (30) minutes) within the previous one (1) month,
 - Deep hematoma diagnosed by imaging techniques within the previous one (1) month,
 - Disseminated malignancies and active cancer (active cancer defined as: cancer for which therapeutic or palliative treatment is either ongoing at the time of enrolment or has stopped less than six (6) months before enrolment),
 - Sepsis, severe infections, pneumonia within the previous 1 month,
 - Known liver cirrhosis,
 - Pregnancy or having delivered within the previous 1 month,
 - Atherosclerotic vascular disease thrombosis within the previous 1 month (e.g. myocardial infarction, stroke, coronary syndrome, peripheral artery disease stage III or IV),
 - Sickle cell disease,
2. Patients presenting with a suspect thrombotic event related to catheter implantation
3. Ongoing therapeutic anticoagulants (curative and preventive regimen) started twenty four (24) hours or more before blood draw (except aspirin and platelet inhibitors)
4. Previous anticoagulant therapy stopped less than three (3) months before blood draw (except aspirin and platelet inhibitors)
5. Patients with previous DVT/PE occurred less than three (3) months from screening.
6. Suspect thrombotic events in other locations at screening, including distal to the knee and upper extremity DVT (based on standard of care examinations)
7. Patients with known tissue plasminogen activator (tPA) deficiency
8. Patient participating or who has participated within one month of enrolment in another investigational study
9. Major co-morbid condition(s) or other reasons that could limit the patient's ability to participate in the study or to comply with follow-up requirements, or impact the scientific integrity of the study.

6. STUDY PROCEDURES

6.1 SCREENING

Prospective, consecutive ambulatory outpatients (presenting to the emergency unit or outpatient clinic) suspected of having VTE will receive an explanation about the study, will be screened for eligibility using the inclusion and exclusion criteria (see Section 5.1). If the patient is eligible, he/she will be

Country-specific amendment for US sites

offered the possibility to participate in the study and go through the informed consent process (see Section 14.1) These patients will then be evaluated using the Wells score and procedures according to SOC for VTE diagnosis at the site.

As patients eligible in this study require emergency procedures/tests to be performed, it is possible that D-Dimer test or VTE diagnosis are completed before the investigator has the possibility to obtain patient written consent to participate in the study. Therefore, **this procedure will not be considered a protocol deviation** as long as the Investigator is blinded to the result of the D-Dimer test or to final VTE diagnosis at the time of patient screening.

The relevant demographic characteristics, medical history and concomitant medication treatment of the enrolled patients will be reported.

Three months follow-up information may be recorded directly in the CRF, in this case the CRF will be considered as Source Document.

A register may be kept for:

- all screening failure patients, including reasons for non-inclusion
- patients screened and satisfying the criteria for inclusion/exclusion but for whom a final VTE diagnosis according to site's SOC is not available will be excluded from the study. These patients will be reported, as well as the reasons for their missing diagnosis.

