6.2 VTE DIAGNOSIS AND STUDY PROCEDURES

At all sites, VTE diagnosis will follow SOC procedures for diagnosis and treatment.

For patients suspected of VTE, this may include imaging only, or D-Dimer test followed by imaging or PTP score + D-Dimer testing + imaging. For all patients for whom VTE is not confirmed by imaging at the initial visit, the study will require that a 3-month follow-up is performed.

- Irrespective of the procedures used locally for VTE diagnosis, sites will be asked to evaluate patients with symptoms consistent with VTE (DVT and/or PE) using the Wells score without knowledge of D-Dimer and/or imaging results. The Wells score result may or may not be used for VTE diagnosis depending on sites' SOC.
- About 12 ml of venous blood will be taken from unlikely subjects (see definition on page 10) in order to obtain at least 6 aliquots of 1 mL of patient plasma each: plasma aliquots will then be banked frozen at -70°C
- STA® - Liatest® D-Di XL will later be used on banked frozen samples to assess assay's accuracy relative to the reference standard (imaging or 3-month follow-up). Only samples determined stable using the procedure described in Section 4.2 will be included in the study.
- Samples may also be used in future studies to evaluate new D-dimer test products to be used as improved diagnostic tools for DVT and/or PE (currently under development by Stago).

Plasma from patients with high Wells score will not be collected in the study.

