6.7 FOLLOW UP

Patients for whom VTE was excluded as per SOC will be followed for 3 months to evaluate potential development of DVT and/or PE.

This follow-up will be performed by the clinician, the study coordinator or the nurse to obtain information regarding development of DVT and/or PE in the 3 months (i.e. 90 days) following Visit 1. The follow-up will have an allowed window of 1 month. Therefore it will take place in the period between 3 and 4 months (i.e. 90 to 120 days) after patient's first visit. The follow-up may be done using several methods according to site choice:

- Phone call to the patient,
- Medical record review if at enrollment patient states he/she does all its medical consultation at the investigation site and if he/she agrees that follow-up will be done by review of its medical record,
- Email to the patient asking the patient to call one site study representative if patient has given its consent to be contacted via email and server for email is secure,
- Call to family doctor in case patient is not answering the call.

The three-months follow-up information may be recorded directly in the CRF, in this case the CRF is considered as Source Document.

In addition, for female patients pregnant at the time of the follow up contact, all efforts will be done to determine if patient had an undetected pregnancy at visit 1, in which case the patient will be excluded from the study due to violation of an exclusion criterion.

If a patient cannot be contacted to collect follow-up information even beyond the 120 days from visit 1, he/she will be considered "lost to follow-up". But before declaring that a patient is "lost to follow-up", the PI (or his/her team) must do his/her best effort to contact patients and attempts should be made via all available routes, and when necessary, patients should be traced through relatives and examination of State death records. A certified letter should be sent to the permanent address on file. The methods used to attempt to contact the patient should be noted.

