9.4 ANALYSIS SETS

The Primary efficacy analysis set will consist of all "unlikely" VTE subjects for whom there are valid observed values on both STA® - Liatest D-Di XL and Reference Standard (imaging or follow up). This includes "unlikely" subjects suspected of PE, or DVT or both; the latter will be included in both of the separate PE and DVT analysis sets. "Unlikely" D-dimer negative subjects having imaging result at Visit 1 will have imaging as reference. Device result is considered valid if it is not missing, its associated QC results are in the QC ranges and is deemed stable after thawing according to criteria provided in Section 4.2. Subjects with major protocol deviations likely to affect outcome will be excluded by blind review³. In line with CLSI guidelines, distal DVT subjects are not included in the primary efficacy analysis set for the DVT indication.

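### Section 6.1 drops eligible patients who have no final standard-of-care diagnosis, although 6.2 and 9.4 would follow and analyse them; the follow-up population needs one definition

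*Combined protocol and SAP*

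**What the plan says.** Five places in the protocol bear on a patient who meets the entry criteria, has a low or moderate Wells score, and leaves the first visit with VTE neither confirmed nor ruled out.

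- **6.1 Screening.** Patients who satisfy the criteria but for whom a final diagnosis under the site's "SOC is not available will be excluded from the study". The next sentence adds: "These patients will be reported, as well as the reasons for their missing diagnosis". Both sentences sit in a list introduced by "A register may be kept for".
- **6.2 VTE Diagnosis and Study Procedures.** "For all patients for whom VTE is not confirmed by imaging at the initial visit, the study will require that a 3-month follow-up" be performed.
- **6.7 Follow Up.** "Patients for whom VTE was excluded as per SOC will be followed for 3 months". The synopsis uses the same scope, for low or moderate Wells patients "for whom VTE is excluded as per site standard of care (SOC) will be followed for 3 months".
- **9.2 Design Considerations.** Follow-up is described for patients excluded at Visit 1 by a negative standard-of-care D-dimer or by negative imaging. The section also describes recruitment as consecutive.
- **9.4 Analysis Sets.** The primary set takes low- or moderate-probability subjects with "valid observed values on both STA® - Liatest D-Di XL and Reference Standard (imaging or follow up"). A final standard-of-care diagnosis is not among its conditions.

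**The concern.** The same patient is treated differently depending on which section is read. Section 6.2 follows the patient and 9.4 then accepts the follow-up outcome as reference. Sections 6.7 and 9.2 and the synopsis do not provide for follow-up, because VTE was not ruled out. Section 6.1 removes the patient altogether.

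This matters because the removal is not random. It depends on how hard the patient was to diagnose, and a consecutive-series accuracy study is meant to avoid that kind of selection. It is also not loss to follow-up as 6.7 defines it (patients who cannot be contacted), since the rule acts before any contact is tried. Section 9.6 promises a general look at dropouts but specifies nothing for this group.

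Three results could be affected. Specificity would be overstated if the dropped patients are mostly device-positive without VTE. Sensitivity and NPV, the co-primary measures, would be overstated if the group includes VTE that the device misses, because those cases would never be counted.

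**Working it through.** **1. The plan's own figures.** Section 9.5 gives PE enrolment as positives divided by prevalence: 75/0.034 = 2,205.9 and 40/0.057 = 701.8, together 2,907.6. The stated 2,908 reproduces. With 115 positives, the smallest number detected that gives an exact two-sided 95% lower limit of at least 0.90 and a point estimate of at least 0.95 is 110 (lower limit 0.901; 109 gives 0.890). At the assumed 98% sensitivity, P(X ≥ 110) = 97.1%, so the claim of at least 90% power holds. With 100 positives it would be 94.9%. These figures do not test the selection question, but they show how much room there is.

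**2. Effect if the dropped patients are device-positive.**

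Inputs from 9.5: 3,054 PE patients, 121 positive, sensitivity 98%. Assumptions not in the documents: specificity 40%, and 2% to 5% of device-positive patients dropped under 6.1.

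- Reference-negatives: 3,054 − 121 = 2,933, so TN = 0.40 × 2,933 = 1,173 and FP = 1,760.
- TP = 0.98 × 121 = 118.6 and FN = 2.4.

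Taking these counts as the complete series and dropping device-positives:

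| Dropped | FP lost | Specificity | TP lost | Sensitivity | NPV |
|---|---|---|---|---|---|
| 0% | 0 | 40.0% | 0 | 98.0% | 99.8% |
| 2% | 35 | 1,173/(1,173 + 1,760 × 0.98) = 40.5% | 2.4 | 116.2/118.6 = 98.0% | 99.8% |
| 5% | 88 | 1,173/(1,173 + 1,760 × 0.95) = 41.2% | 5.9 | 112.7/115.1 = 97.9% | 99.8% |

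NPV = TN/(TN + FN) contains no device-positive patients, so it cannot change here. Sensitivity moves by about 0.1 point, against the sponsor.

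If the 3,054 are instead what remains after the exclusion, restoring the dropped patients gives specificity 1,173/(1,173 + 1,760/0.98) = 39.5% and 1,173/(1,173 + 1,760/0.95) = 38.8%. The difference from 40.0% is again 0.5 and 1.2 points.

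**3. Effect if the group contains VTE that the device misses.**

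Base: 2,908 patients with 115 positives, sensitivity 98%, specificity 40%. Patients are added back with follow-up as reference. Assumed ranges: 1% to 5% of 2,908 excluded, 70% to 90% of them device-positive, VTE prevalence among them 4% to 20%, device sensitivity among them 80% to 98%.

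- Over this range, sensitivity lies between 94.4% and 98.0%, NPV between 99.3% and 99.8%, and specificity between 38.6% and 40.0%.
- If the device detects 98% in this group too, sensitivity stays at 98.0% and NPV moves by less than 0.1 point.
- The worst corner is 5% excluded, 20% prevalence and 80% device sensitivity. It adds 0.05 × 2,908 = 145.4 patients with 29.1 VTE cases, of which 23.3 are detected. Sensitivity is (112.7 + 23.3)/(115 + 29.1) = 136.0/144.1 = 94.4%. This is the only combination examined that falls below the 0.95 point-estimate goal.

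**The case against.** The strongest reply is that 6.1 acts first. Once undiagnosed patients are out, everyone left has VTE either confirmed or ruled out, so the scopes of 6.2 and 6.7 describe nearly the same people. Section 6.7 also does not say that only those patients are followed. This is a fair reading. It makes it uncertain that two sites would really build different sets, which a reader might otherwise infer. It does not remove the selection: on this reading the plan still drops eligible patients because they were hard to diagnose, on a condition that 9.4 does not use.

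A second reply is that 6.1 promises to report these patients and their reasons. That makes the loss partly visible. But the promise sits under a register that sites may choose not to keep, and a count supplies no outcome.

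A third reply concerns the remedy. Sections 6.8 and 6.9 leave treatment unrestricted. A patient treated without a diagnosis who stays event-free would be scored reference-negative, and a true positive could become a false positive. This stands, and it argues against simply deleting the exclusion.

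Two stronger readings are tempting and not supported.

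- **The dropped patients are mostly D-dimer-positive.** This is plausible where local practice uses D-dimer, since 2.2 and 9.2 treat a low- or moderate-probability patient with a negative result as ruled out. But 6.2 also allows imaging-only pathways, the local assay is not the study device, and no figure is given.
- **The rule uses up the margin between 121 and 115 PE positives.** The 121 in 9.5 are counted as PE-positive and so already have a reference result. Patients dropped for want of a diagnosis lie outside that count and cannot be subtracted from it.

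**Conclusion.** The inconsistency is real and should be corrected; its numerical effect is probably small. If the affected patients are mainly device-positive, specificity is overstated by about 0.5 to 1.2 points, assuming 2% to 5% of device-positives are affected and 40% specificity. Specificity is a secondary estimate without a performance goal. NPV is then unchanged and sensitivity shifts by about 0.1 point.

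The co-primary measures are threatened only if the group holds VTE that the device misses, and a missed sensitivity goal appeared only in the extreme corner of an assumed range. It cannot be excluded without the count. There is no evidence of a power problem: power at 115 positives is about 97%.

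**What to change.** 1. Use one follow-up population. Carry the 6.2 scope (VTE not confirmed by imaging at the initial visit) into the synopsis, 6.7 and 9.2, and reword 6.1 to match.
2. Keep consented, sampled low- or moderate-probability patients without a final standard-of-care diagnosis in 3-month follow-up, and flag them in the database.
3. Report sensitivity, NPV and specificity with and without the flagged patients, identifying those anticoagulated without a diagnosis. Write this into both SAPs before the device results are merged at data lock, as 9.2 already provides, so that the choice is made blind.
4. Make the count of these patients and the reasons for the missing diagnosis mandatory, independent of the optional register.
5. For DVT, apply this to the enrolment still under way. For PE, where collection is complete and data are being cleaned, include such patients only where banked plasma and a 90-day outcome exist, and report how many cannot be included. Nothing in the documents shows how many that would be.

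The cost is wording in a few sections and some extra contacts of a kind sites already make. The reference is weaker for patients treated without a diagnosis, which is why the flag and the paired analyses are needed. Specificity may come out slightly lower.
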